 - ii. Describe reasons for discontinuation of CAB LA PrEP
 - iii. Describe characteristics of the individuals who discontinue CAB LA PrEP
- 3) Effectiveness: Monitor for incidence of HIV diagnoses while on CAB for PrEP and describe the timing of incident HIV diagnoses with respect to timing of CAB for PrEP usage
 - a. Describe the proportion and number of incident HIV-1 infections while on CAB for PrEP among individuals in the following groups:
 - i. Infected during OLI
 - ii. Infected while on CAB LA: Incident HIV diagnoses, defined as HIV diagnosed after start of CAB injections while adhering to CAB LA PrEP regimen
 - b. Describe the timing of diagnosis of HIV with respect to timing of CAB for PrEP usage among individuals in the following groups:

- i. Infected during OLI
- ii. Infected while on CAB LA: Incident HIV diagnoses while adhering to CAB LA PrEP regimen
- c. Describe the proportion of incident infections among those who start with OLI and those who go to DTI separately and the timing of diagnosis of incident HIV for the overall group, and separately for the OLI and DTI groups.

The proposed study is a non-interventional study and will collect data from routine clinical practice and plans to capture all prevalent HIV-1 infections, including those captured during baseline. However, there are no plans to collect and store serum samples for subsequent testing as this is not part of standard of care.

- 4) Safety: Monitor for occurrence of DILI and HSRs following CAB LA injections
 - a. Describe the frequency of DILI after starting CAB LA at 6, 12, 24, 36, and >36 months after initiation as defined in Section 7.3.2.
 - i. Incidence proportion and rate of DILI following administration of CAB LA PrEP
 - ii. Incidence proportion and rate of CAB LA discontinuation due to DILI
 - b. Describe the frequency of HSR after starting CAB LA at 6, 12, 24, 36, and >36 months after initiation
 - i. Incidence proportion and rate of HSR following administration of CAB LA PrEP
 - ii. Incidence proportion and rate of CAB LA discontinuation due to HSR
- 5) Resistance: Evaluate incidence of and risk for developing resistance to integrase inhibitors (INSTI) among individuals in the following groups:
 - a. Incident HIV diagnoses while adhering to CAB LA for PrEP and development of resistance during treatment for HIV
 - b. CAB LA PrEP discontinued:
 - i. without subsequent oral PrEP & potential risk for HIV acquisition and viral resistance during CAB LA PK tail

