7.2. Study Population and Setting

7.2.1. Study Setting

Potential investigational sites within the NEAT-ID Network across Europe will be contacted for feasibility and resistance testing practices as part of their SoC. A formal feasibility assessment questionnaire will be conducted after the protocol is finalized and approved and will be used to determine sites' eligibility to participate in the study. This formal feasibility assessment will include assessing site's infrastructure to participate in research studies, number of any PrEP prescriptions in the previous year, availability of resistance testing, and HIV testing practices per local standard of care practices. Followup period will start from the date of the first participant enrolled in the study and will end five years after the date of first enrolment.

Participant data will be collected via extraction from electronic medical records (i.e., source data) by appropriately trained and authorized member(s) of the study team who must be identified and authorized in writing by the Principal Investigator (PI). A delegation of responsibility log will be maintained accordingly. In order to maintain confidentiality, the participants will be identified only by study number.

All data will be entered directly into the electronic data capture (EDC) by the sites and will be checked for completeness every 6 months by the data coordinating center. NEAT-ID's management team will store the data on a secure network drive with access to authorized personnel of the data management team only, maintained on a log of authorized personnel by the data coordinating center.

NEAT-ID team will perform site management activities to assess protocol issues, consent, data quality and study management quality performance.

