7.4.1. Study size

The study is not a hypothesis testing study, but it is designed to assess usage of CAB LA for PrEP in real world clinical settings. The overall number of participants in this cohort study will depend on the uptake of the CAB LA for PrEP and how widely it will be used across the NEAT-ID clinical sites.

The study aims to include a target of at least 500 participants initiating CAB LA for PrEP. There is no formal statistical hypothesis to be tested in these analyses. Table 1 below gives an indication of the likely precision of the estimates of the proportion with incident HIV, using Exact Clopper Pearson confidence limits under different scenarios.

Confidence Level	Sample Size (N)	CI Width	Incident HIV rate (%)	Lower Limit	Upper Limit
0.95	500	1.1824	0.25	0.0118	1.1942
0.95	500	1.5093	0.50	0.0832	1.5925
0.95	500	1.9926	1.00	0.3255	2.3181
0.95	500	2.3679	1.50	0.6283	2.9962
0.95	500	2.6841	2.00	0.9631	3.6472
0.95	500	2.9617	2.50	1.3185	4.2802
0.95	1000	0.7568	0.25	0.0416	0.7984
0.95	1000	1.0004	0.50	0.1625	1.1629
0.95	1000	1.3507	1.00	0.4806	1.8313
0.95	1000	1.6201	1.50	0.8419	2.4620
0.95	1000	1.8462	2.00	1.2258	3.0720
0.95	1000	2.0442	2.50	1.6243	3.6685
0.95	2000	0.5012	0.25	0.0812	0.5824
0.95	2000	0.6776	0.50	0.2400	0.9176
0.95	2000	0.9283	1.00	0.6119	1.5402

Table 1: Precision estimates

CONFIDENTIAL

CTMS Project Number: 221935 Final Protocol

				-	
0.95	2000	1.1202	1.50	1.0143	2.1345
0.95	2000	1.2810	2.00	1.4326	2.7136
0.95	2000	1.4217	2.50	1.8611	3.2828

Table 2 below shows the precision estimates for regimen discontinuation rates varying from 2.5% to 20% for a sample of 500 individuals.

Confidence Level	Sample Size (N)	CI Width	Discontinuation rate	Lower Limit	Upper Limit
0.95	500	0.0296	0.025	0.0132	0.0428
0.95	500	0.0403	0.050	0.0326	0.0729
0.95	500	0.0546	0.100	0.0751	0.1297
0.95	500	0.0646	0.150	0.1198	0.1844
0.95	500	0.0720	0.200	0.1658	0.2378

 Table 2. Precision estimates by discontinuation rate

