7.6. Data analysis

7.6.1. Essential analysis

Specific analytic methods are shown for each study objective. All CAB LA PrEP users will be followed for at least 3 years (36 months). All individuals with incident HIV acquisition will be followed through the end of the follow-up period. Participants discontinuing CAB LA PrEP will be monitored through the end of the follow-up period for HIV acquisition and, in the case of HIV acquisition, will be monitored for ART effectiveness and potential emergence of resistance.

In the event of a delay of ART initiation post HIV diagnosis, the study team will strive to follow the individual through the end of the follow-up period. Interim results will be generated at 12, 24, 36, 48 months since study initiation and final results will be generated at 60 months since study initiation.

Analysis for Objective 1 (Description of CAB for PrEP Usage pattern)

For individuals initiating CAB for PrEP, baseline demographics (age, sex, gender, ethnic origin (where available), BMI, geographic region), history of previous PrEP use and use of OLI prior to initiating injections will be described. Comorbidities, STIs, risk factors for HIV acquisition (e.g. HIV status of sexual partner, multiple sexual partners), will be reported as frequencies at baseline and at 6, 12, 24, 36, and >36 months of follow-up as available. Proportion of individuals using oral PrEP to cover planned, delayed or missed CAB LA injections will also be provided. Frequency of testing for HIV once initiated CAB for PrEP will be evaluated, and timing of HIV testing relative to injection dates will be assessed.

Prevalent HIV is defined as any undiagnosed HIV at the time of PrEP initiation and will be defined as positive HIV antigen/antibody test and/or positive viral load from sample collected at the time of initiation (first prescription of CAB oral lead and, separately, first CAB LA PrEP injection). Note the test result may be reported within 4-6 weeks after the sample was collected. Prevalent HIV will be reported at baseline while on CAB OLI and while on CAB LA. Also, prevalent HIV will be reported for those who received CAB OLI and separately for those with direct to injection (DTI) strategy. Incident HIV is any new HIV diagnosis that occurs after the initiation of CAB PrEP, having confirmed HIV negative status using HIV RNA test, at the time of PrEP initiation. Incident HIV reporting is described in objective 3.

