Frequency of undiagnosed prevalent HIV at CAB PrEP initiation will be assessed as described for objective 1. The primary effectiveness measure for objective 3 is proportion of individuals with incident HIV diagnosis during OLI and separately during CAB LA PrEP and will be calculated at 6, 12, 24, 36 months and over the entire length of follow-up. The proportion of incident infections among those who start with OLI and those who go to DTI will also be reported separately along with the timing of diagnosis of incident HIV acquisition for the overall group, and separately for the OLI and DTI groups.

Adherence patterns and characteristics of individuals with incident HIV diagnosis will be compared with those without incident HIV diagnosis, using t-test for continuous variables (Wilcoxon rank sum test for not normally distributed variables) or chi-square test for categorical variables. Participant characteristics significantly impacting acquisition of HIV based on univariate analysis will be selected for multivariable analysis. Risk for HIV acquisition and characteristics affecting risk for HIV acquisition will be assessed using negative binomial model with log-link function with binary outcome (HIV diagnosis vs not) if feasible.

Time to HIV diagnosis will be defined as time from first CAB LA PrEP injection to the first HIV diagnosis using laboratory antigen/antibody test, confirmed by viral RNA test. Time to HIV diagnosis will be assessed using Kaplan-Meier curve. Differences in time to diagnosis will be assessed by sex, gender, ethnicity (where available), geographic region, and risk factors (e.g. STI, previous PrEP usage) related, adherence to current PrEP to HIV acquisition. Additionally, time to diagnosis will be shown for people who acquired the infection while prescribed oral CAB lead in (if applicable). Time to diagnosis in this group will be defined as time from first CAB oral prescription to the first positive HIV-1 antigen/antibody lab result, confirmed by viral RNA test.

If feasible, Cox proportional hazards models will be constructed to compare time to HIV diagnosis by subgroup adjusting for additional variables (e.g., sex, ethnicity, (where available) geographic region).

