ART regimen and VL testing among CAB PrEP users with undiagnosed prevalent infections and incident infections will be described separately, during the follow-up period. In the event of a delay of ART initiation post HIV diagnosis, the study will strive to follow the individual after ART initiation and through the end of the follow-up period. Durability of INSTI-based vs. non-INSTI based regimens (e.g., the numbers and proportions of those who achieve and maintain virologic suppression, the time to virologic breakthrough), as well as any INSTI resistance-associated substitutions that are detected upon ART failure will also be assessed and reported.

Analysis for Objective 4 (Safety: Monitor for occurrence of DILI and HSR)

Proportion and number of individuals with DILI and HSRs following CAB OLI and CAB LA injections will be shown separately at 6, 12, 24, 36 months after initiation and over the entire length of the follow-up period. Proportion and number of individuals discontinuing CAB OLI and CAB LA PrEP due to DILI or HSR will be shown at 6, 12, 24, 36 months and over the entire length of the follow-up period. Discontinuation of CAB LA PrEP or CAB OLI will be based on medical records indicating date when discontinuation decision was made by a physician and will be reviewed and confirmed by an independent adjudication committee. Frequency of hepatotoxicity and HSR events will be reported separately for OLI period and during injections.

Analysis for Objective 5 (Resistance monitoring)

Proportion and number of individuals developing drug resistance to INSTIs based on genotypic data will be assessed among the 4 different groups as follows:

a) Individuals with undiagnosed prevalent HIV, initiating CAB OLI or CAB LA PrEP, will be followed through the end of the follow-up period after ART initiation and will be monitored for resistance

- b) Individuals with incident HIV while on CAB LA PrEP will be followed through the end of the follow-up period following ART initiation and monitored for resistance
- c) Individuals who discontinue CAB LA PrEP will be followed through the end of the follow-up period and if they acquire HIV will continue to be followed after ART initiation to monitor for resistance
- d) Individuals who switch to oral PrEP and acquire HIV during the 12- month follow-up period while on oral PrEP will be followed through the end of the follow-up period after ART initiation and monitored for resistance

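### The primary HIV measure is a simple proportion with no stated denominator at each horizon, no HIV rate per person-year is planned, and the DILI and HSR rates promised in Section 6 are missing from the analysis

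*Protocol*

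**What the plan says.** - **Primary measure (Section 7.6.1, Objective 3).** "The primary effectiveness measure for objective 3 is proportion of individuals with incident HIV diagnosis during OLI and separately during CAB LA PrEP". It "will be calculated at 6, 12, 24, 36 months and over the entire length of follow-up". The number of people to be placed in the denominator at each horizon is not given.
- **Precision (Section 7.4.1).** "Table 1 below gives an indication of the likely precision of the estimates of the proportion with incident HIV". The limits are Clopper-Pearson limits on the full N of 500, 1000 or 2000.
- **Follow-up.** Section 7.2.1 says that the follow-up period "will end five years after the date of first enrolment". Section 7.6.1 says "All CAB LA PrEP users will be followed for at least 3 years (36 months". Section 7.8 leaves the pace of data collection to market uptake and expects loss to follow-up. Section 7.5 keeps people who discontinue under observation to the end.
- **Interim reports (Section 7.6.1).** "Interim results will be generated at 12, 24, 36, 48 months since study initiation".
- **Time to event.** The Synopsis lists time to incident HIV diagnosis among the primary outcomes, and Section 7.6.1 assigns it a Kaplan-Meier curve.
- **Rates.** Section 5.1 quotes 0.40 and 0.20 per 100 PY on cabotegravir in the two pivotal studies. No rate per person-year is planned for HIV. For safety, Section 6 promises "Incidence proportion and rate of DILI following administration of CAB LA PrEP", and the same for HSR, but the Objective 4 analysis says only "Proportion and number of individuals with DILI and HSRs following CAB OLI and CAB LA injections will be shown separately".

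**The concern.** A proportion at a fixed horizon describes risk only if everyone in the denominator was observed to that horizon or had the event. Here people enter at different times, some are lost, and the annual interim reports fall before many can reach the later horizons. Without a stated denominator, two analysts could follow the protocol faithfully and report figures that err in opposite directions. The figure over all follow-up has no fixed time base, because it pools people observed for different lengths of time. None of these proportions can be set beside the pivotal results, which are per 100 PY. For liver injury and hypersensitivity, an objective and its analysis section do not match.

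**Working it through.** **1. The plan's own table.** For N = 500 and 1.00% (5 cases), the Clopper-Pearson limits from beta quantiles are 0.3255% and 2.3181%, as printed. All rows of Tables 1 and 2 reproduce, apart from one difference of 0.0001 in a lower limit (0.0119 against 0.0118 at N = 500, 0.25%). The tables are right for 500 people with complete follow-up. They make no allowance for incomplete follow-up.

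**2. Inputs.** From the protocol: N = 500, HIV rate λ = 0.004 per year (0.40 per 100 PY), horizon 3 years, close at 5 years. The three-year minimum then implies entry over 5 − 3 = 2 years. My assumptions: constant hazards, uniform entry, and non-informative stopping or loss of a fraction s per year, with μ = −ln(1 − s). The documents give no loss rate, and Table 2 gives discontinuation of 2.5% to 20% without a time base, so a range is shown.

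**3. Final analysis at 36 months.** Target risk = 1 − exp(−3λ) = 1.193%.
- All initiators as denominator: P = λ/(λ+μ) × [1 − exp(−3(λ+μ))].
- Cases plus completers as denominator: P / (P + C), with C = exp(−3(λ+μ)).

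| s per year | P | Ratio to 1.193% | C | P/(P+C) |
|---|---|---|---|---|
| 0% | 1.193% | 1.00 | 98.81% | 1.19% |
| 5% | 1.106% | 0.93 | 84.71% | 1.29% |
| 10% | 1.023% | 0.86 | 72.03% | 1.40% |
| 20% | 0.870% | 0.73 | 50.59% | 1.69% |

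For s = 10%: μ = 0.10536 and P = 0.004/0.10936 × (1 − exp(−0.32808)) = 0.03658 × 0.2797 = 1.023%. The completers version is 1.023/(1.023 + 72.03) = 1.40%. In simulations at 10% and 20%, Kaplan-Meier returned 1.18% and 1.19%, and the person-time rate was 0.40 per 100 PY in both.

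With all initiators, the shortfall is 1.193 − 1.023 = 0.17 points at 10% and 1.193 − 0.870 = 0.32 points at 20%. In 500 people that is about 0.9 and 1.6 events.

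**4. Staggered entry alone (no loss).** With entry over 2 years, everyone has 36 months by the close, so the final 6 to 36 month figures have ratio 1.00. If entry ran over 3 or 4 years, the final 36-month ratio would be 0.94 or 0.83.

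At the interims, if an unreached horizon were tabulated over everyone enrolled so far:
- 12-month risk at month 12: 0.20% against 0.40%, ratio 0.50.
- 24-month risk at month 24: 0.40% against 0.80%, ratio 0.50.
- 36-month risk at month 36: 0.80% against 1.19%, ratio 0.67.
- 36-month risk at month 48: 1.09% against 1.19%, ratio 0.92.

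**5. Entire follow-up.** It mixes 3 to 5 years. With no loss the proportion is 1.59%, between the 3-year risk of 1.19% and the 5-year risk of 1.98%.

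**6. Precision in person-time.** 500 × 3 = 1500 PY, and 1500 × 0.004 = 6 cases. The exact Poisson limits are χ²(0.025; 12)/2 = 2.20 and χ²(0.975; 14)/2 = 13.06, so the rate is 0.40 per 100 PY (95% CI 0.15 to 0.87). At 0.20 per 100 PY, 3 cases give 0.04 to 0.58.

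**The case against.** A good deal can be said for the plan, and much of it stands.

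- **A censoring-aware analysis is already planned.** Time to HIV diagnosis is a listed primary outcome with a Kaplan-Meier curve. A reader might infer that censoring is ignored or treated only as secondary; the Synopsis does not support that. What remains is that the measure named as primary for effectiveness is the simple proportion, and the horizon figures are not tied to the curve.
- **Direction.** A reader might conclude that the proportion is biased low. That follows only if all initiators are counted, as the use of full N in Table 1 suggests. The protocol does not say so, and a completers denominator errs upward.
- **Staggered entry.** A reader might think that it spoils the final figures. If the three-year minimum is kept, it does not (step 4). The minimum and the five-year close are compatible if enrolment ends by month 24. The visible text does not state that limit, but the milestone table is partly redacted, so its absence cannot be asserted.
- **Interim ratios.** The 0.50 and 0.67 apply only if unreached horizons are reported over everyone enrolled. Section 7.6.1 does not say that they will be.
- **Stopping is not plainly an error.** The probability of a diagnosis while on cabotegravir, with stopping as a competing event, is a legitimate quantity. Kaplan-Meier with censoring at stopping answers a different question, the risk had nobody stopped, and needs stopping to be unrelated to HIV risk, which is doubtful here. Loss and unreached horizons do not have this defence.
- **Size.** The final shift is well inside the 1.99-point width of the Table 1 interval at 1%. The study tests no hypothesis and plans no formal comparison with the pivotal rates.

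**Conclusion.** The point holds in a limited form. The primary effectiveness measure ignores unequal time at risk and has no stated denominator, so its value depends on an unstated choice. At 36 months it could be about 0.93 of the true risk (all initiators, 5% loss per year), 0.86 (all initiators, 10% stopping or loss per year, if the target is the risk had nobody stopped), or 1.40% against 1.19% (completers, 10% per year). The entire-follow-up figure has no single time base. These sizes rest on assumed constant hazards, uniform entry and assumed stop/loss rates. In absolute terms the final effect is one or two events in 500; the interims could be further off if unreached horizons are tabulated.

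Two parts need no assumption: no HIV rate per person-year is planned, and the DILI and HSR rates promised in Section 6 are absent from the Objective 4 analysis in Section 7.6.1. The documents do not support saying that the reported HIV risk will be too low, that Tables 1 and 2 are miscalculated, or that the follow-up statements contradict each other.

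**What to change.** 1. In Section 7.6.1, make the primary effectiveness measure the incident HIV rate per 100 PY on cabotegravir with an exact Poisson 95% CI, together with risks and 95% CIs at 6, 12, 24 and 36 months read from the Kaplan-Meier analysis already planned. State that this censors at stopping and assumes stopping is unrelated to HIV risk, or use a cumulative-incidence estimator with stopping as a competing event. Keep the raw counts, with the denominator stated.
2. At interims, report only horizons that have participants at risk.
3. Carry the person-time rates for DILI and HSR from Section 6 into the Objective 4 analysis.
4. Add a person-year precision row to Table 1, for example 6 cases in 1500 PY: 0.40 per 100 PY, 95% CI 0.15 to 0.87.
5. Reconcile the three-year minimum with the five-year close by stating in Section 7.2.1 that enrolment ends by month 24. The follow-up commitment should be kept, not loosened.

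The cost is wording and a few more tables. Injection dates and laboratory data are already collected. Reported risks may look slightly less favourable than a proportion of all initiators would.

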Analysis for Objective 2 (Monitor for adherence by assessing the frequency of delayed and missed injections without oral PrEP bridging)

Adherence will be estimated using the dates of injections. Proportion and number of individuals with ≥ 1 delayed (≥ 7 days)and/or ≥ 1 missed injection without oral PrEP bridging over 6, 12, 24, 36, >36-month periods will be provided. Additionally, mean (median) number of delayed and missed injections will be provided for each period. Proportion and number of individuals with ≥ 7 days delay of CAB LA PrEP injection over 6, 12, 24, 36, >36-month periods will be provided. Additionally, mean (median) number of days delayed will be provided for each period.

Characteristics of persons with delayed or missed injections without oral PrEP bridging will be compared with those that are on time with the injections for 6, 12, 24, 36, and >36-month periods using t-test for continuous variables (Wilcoxon rank sum test for not normally distributed variables) or chi-square test for categorical variables.

Proportion and number of individuals who discontinue CAB LA PrEP over 6, 12, 24, 36, and >36-month-periods and overall will be provided. Additionally, distribution of individuals who discontinued by most common discontinuation reasons will be provided and will be used to understand whether individuals are missing injections or choosing to discontinue the regimen. Characteristics of persons who discontinue vs persons who stay on therapy will be compared for 6, 12, 24, 36, and >36-month periods using t-test for continuous variables (Wilcoxon rank sum test for not normally distributed variables) or chi-square test for categorical variables.

If feasible, risk of delayed or missed injections and separately risk of discontinuation will be assessed using negative binomial model with log-link function accounting for sex, age group, race/ethnicity, and other characteristics found significant in univariate analysis.

Analysis for Objective 3 (Effectiveness: Monitor for incidence of HIV diagnoses while on CAB for PrEP)

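### Objective 3 relates adherence to HIV diagnosis without aligning exposure time, so the association is distorted even under no effect, in a direction set by how injections after diagnosis are counted

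*Protocol*

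**What the plan says.** All references are to the protocol.

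- **Comparison by HIV status (section 7.6.1, Objective 3).** "Adherence patterns and characteristics of individuals with incident HIV diagnosis will be compared with those without incident HIV diagnosis, using t-test for continuous variables", with Wilcoxon or chi-square tests as alternatives. No feasibility condition is attached. Characteristics significant in univariate analysis go forward to a "negative binomial model with log-link function with binary outcome (HIV diagnosis vs not) if feasible".
- **Time to diagnosis (same place).** "Time to HIV diagnosis will be assessed using Kaplan-Meier curve", with time zero at the first injection. Differences are to be assessed by sex, gender, ethnicity, region and "risk factors (e.g. STI, previous PrEP usage) related, adherence to current PrEP to HIV acquisition". The wording is garbled, but adherence is clearly one of the listed factors.
- **Cox model (same place).** If feasible, "Cox proportional hazards models will be constructed to compare time to HIV diagnosis by subgroup adjusting for additional variables". Adherence is not named in that sentence.
- **Adherence measures (sections 7.3.2 and 7.6.1, Objective 2).** These are having at least one late (7 days or more) or missed injection, the number of such injections, and the length of delay. Objective 2 reports them in windows: "missed injection without oral PrEP bridging over 6, 12, 24, 36, >36-month periods will be provided". Objective 3 does not refer to these windows.
- **Follow-up and case definition.** People with incident HIV are followed to the end of the study (section 7.6.1). Sections 6 and 7.3.2 tabulate infections on CAB LA as those arising in people keeping to the regimen. Section 7.3.2 also gives a broader definition: any new diagnosis after a negative RNA test at initiation.

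**The concern.** Lateness builds up after baseline, and the chance of ever being late grows with the number of injections that have fallen due. HIV diagnosis cuts that number short. Comparing ever-late status or counts between people with and without HIV therefore compares short exposure histories with long ones. A Kaplan-Meier split from first injection needs groups known at first injection, when no injection can yet be late. If later lateness defines the groups, HIV-free time before the first late injection is credited to the late group.

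Section 5.2 names non-adherence as a risk for HIV acquisition, and cumulative results are reported every year. An artefact that makes late injections look harmless, or far more harmful than they are, would bear on that risk. It could also pass through the univariate screen into the multivariable model.

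**Working it through.** **The plan's own figure.** The protocol gives no figure for this comparison. Its Table 1 (exact Clopper-Pearson limits for the proportion with HIV) reproduces: N=500 at 1.00% gives 0.3255% to 2.3181%, and all 18 rows agree to within 0.0001 percentage point. That primary proportion does not involve adherence.

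**Inputs from the protocol.** Injections at months 0 and 1, then every 2 months (section 5.1). Follow-up of at least 3 years, ending 5 years after first enrolment (sections 7.6.1 and 7.2.1). HIV incidence on CAB of 0.40 and 0.20 per 100 PY (section 5.1). Target of at least 500 (section 7.4.1).

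**Assumptions.** The protocol gives no late probability *p* per injection and no effect of lateness. I take *p* = 5% and 10%.

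**Step 1: unequal opportunity.** By month 8, follow-on injections were due at months 1, 3, 5 and 7 (4 in all). By month 12 there are 6, and by month 36 there are 18. At *p* = 10% the chance of ever being late is 1 − 0.9^4 = 34%, 1 − 0.9^6 = 47% and 1 − 0.9^18 = 85%. A common 12-month window narrows the gap for someone diagnosed at month 8 but does not close it.

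**Step 2: hand calculation under no effect, counting up to diagnosis.** Take *n* = 24 injections due (4 years, one every 2 months) and a rare diagnosis equally likely in any interval.

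- Ever late, no HIV: 1 − (1−p)^n
- Ever late, HIV: 1 − [1 − (1−p)^n]/(np)
- Apparent ratio: (ever late, HIV ÷ ever late, no HIV) ÷ (never late, HIV ÷ never late, no HIV)

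| p | (1−p)^24 | Ever late, no HIV | Ever late, HIV | Apparent ratio |
|---|---|---|---|---|
| 10% | 0.080 | 92.0% | 1 − 0.920/2.4 = 61.7% | (0.617/0.920)/(0.383/0.080) = 0.14 |
| 5% | 0.292 | 70.8% | 1 − 0.708/1.2 = 41.0% | (0.410/0.708)/(0.590/0.292) = 0.29 |

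**Step 3: simulation.** 400,000 people, follow-up uniform over 3 to 5 years, 0.40 per 100 PY unless stated, adherence counted up to diagnosis, fixed ever-late group.

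| Scenario | True rate ratio | Fixed-group HR |
|---|---|---|
| 10% late | 1 | 0.16 (ever late 61% of cases, 90% of others; mean late injections 1.14 and 2.25) |
| 5% late | 1 | 0.30 |
| 10% late, 0.20 per 100 PY | 1 | 0.16 |
| 10% late, 5% stopping per interval | 1 | 0.24 |
| 10% late on average, concentrated in few people | 1 | 0.63 |
| 10% late | 3 | 0.21 |
| 10% late on average, concentrated | 3 | 0.96 |

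**Step 4: injections not given after diagnosis counted as missed.** At 10% late and no effect, 99.4% of cases become ever late or missed, against 90.0% of others: (0.994/0.900)/(0.006/0.100) = 18. The mean counts are 12.7 and 2.2. The size is unstable because almost no cases remain in the never-late group (about 11 to 55 in the other no-effect scenarios), but the direction is the same in all of them.

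**Step 5: alternatives.** At 10% late:

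- The late share of injections due is 9.9% in cases and 10.0% in others under no effect.
- Time-updated lateness gives 1.00 when the true ratio is 1, and 3.04 when it is 3.
- A 12-month landmark gives 1.02 under no effect. With a true ratio of 3 acting only in the interval after a late injection, it gives 1.04: it removes the artefact but misses a short-lived effect.

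**Step 6: expected cases at N=500.** 500 × 3 × 0.0040 = 6 and 500 × 5 × 0.0040 = 10. At 0.20 per 100 PY, 3 and 5.

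**The case against.** The strongest reply is that the protocol is silent rather than wrong. It never says that adherence is summed over the whole follow-up or held as a fixed group, and coding a time-varying covariate is commonly left to the analysis plan. The study tests no hypothesis, the primary effectiveness measure is unaffected, few cases are expected and the regression models are conditional on feasibility. All of this limits the severity. It does not remove the point: the comparison by HIV status and the listing of adherence as a factor for time to diagnosis are commitments without a feasibility condition, and no adherence measure in the protocol has injections due or person-time as its denominator.

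Four stronger readings are tempting, and the document does not support them:

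- **The bias always makes lateness look protective.** It does so only if counting stops at diagnosis, which is not stated. Counting over all follow-up reverses it.
- **Adherence is explicitly a fixed whole-follow-up group.** This is an inference from the methods named.
- **The Cox model enters adherence as a fixed term.** The Cox sentence does not mention adherence.
- **Objective 2 has the same immortal-time fault.** "Characteristics of persons with delayed or missed injections without oral PrEP bridging will be compared with those that are on time", but the sentence goes on to specify 6- to 36-month and longer periods, and there is no survival outcome. Some unequal opportunity remains within windows; that is a different and smaller matter.

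**Conclusion.** The point holds as a should-fix. As written, Objective 3 relates post-baseline adherence to HIV with nothing to align exposure time. With no true effect, the text allows a fixed-group hazard ratio anywhere from about 0.16 to 0.63 (counting up to diagnosis) to about 18 (counting afterwards). Under the first reading, a real tripling of risk is reversed or hidden. The sizes rest on assumed late probabilities of 5-10% and on how lateness is spread between people. The existence of the distortion rests only on the chance of ever being late growing with the number of injections due.

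The case definition adds a separate circularity. If only infections in people keeping to the regimen are counted, cases arising in late or missed time may be left out of the very comparison meant to assess adherence. Section 7.3.2 contains both the narrow and the broad definition, and Objective 3 does not say which governs this comparison.

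**What to change.** In section 7.6.1, Objective 3:

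1. Count adherence only up to HIV diagnosis. In the comparison by HIV status, express it per injection due or per person-time.
2. For time to diagnosis, replace the plain Kaplan-Meier split by adherence with time-updated adherence. Divide follow-up into on-time, late or missed, and bridged person-time, and report HIV events per 100 PY in each state. A landmark analysis is a simpler alternative, with the limit shown in step 5.
3. If adherence enters a Cox model, enter it only as a time-dependent covariate.
4. For this comparison, count incident HIV whatever the adherence at diagnosis, using the broader definition in section 7.3.2. Keep the narrower tabulation as a separate description.

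The cost is revised wording and some counting-process programming. Injection dates are already collected (section 7.5). With about 3 to 10 expected cases the estimates will be imprecise, and reports should say so. The change is best made before the 12-month interim results.
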